- G: PRO QoL assessments will be completed for the last time at the visit that the subject consents to Amendment 1 (ie, Month 12, Month 18, Month 24, or Month 30). If consent into Amendment 1 and switching to CSL312 200 mg AI is performed at an unscheduled visit after the Month 12 Visit, the last data for PRO QoL assessments will be from the last visit prior to the unscheduled visit (under the original protocol).
- H: Urine collection for urinalysis will be collected for the last time at the visit that the subject consents to Amendment 1 (ie, Month 12, Month 18, Month 24, or Month 30). If consent into Amendment 1 and switching to CSL312 200 mg AI is performed at an unscheduled visit after the Month 12 Visit, the last data for urinalysis will be from the last visit prior to the unscheduled visit (under the original protocol).
- I: On a visit day, blood draws should be completed on the same day of CSL312 administration.
- J: Per Amendment 1, collection of blood sample for hematology / biochemistry / coagulation analysis will be required every 12 months starting from the Month 12 Visit.
- K: Blood samples for potential future assessment of HAE biomarkers will be obtained for the last time at the visit that the subject consents to Amendment 1 (ie, Month 12, Month 18, Month 24, or Month 30). If consent into Amendment 1 and switching to CSL312 200 mg AI is performed at an unscheduled visit after the Month 12 Visit, the last collection of HAE biomarkers will be from the last visit prior to the unscheduled visit (under the original protocol). These samples will be stored for potential future assessment of HAE biomarkers and will be destroyed within 5 years after completion of the study. These samples will not be collected in adolescents.
- L: The urine test for beta-human chorionic gonadotropin will be performed only for women of childbearing potential. A serum pregnancy test will be performed by the site if urine result is inconclusive. Female subjects of childbearing potential will perform home urine testing on months for which there is no onsite visit.
- M: At the Follow-up Visit (conducted via telephone call), HAE attacks will be reported verbally, as the eDiary is deactivated at the End of Treatment Visit.

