7.1 Treatment Descriptors

For efficacy, PK and PD analyses (see [Section 10](#)) all subjects regardless of used administration device (NSD or AI) will be displayed under the 200mg CSL312 dose. Per the original protocol it was planned that for safety, PK and PD analyses (see [Sections 11, 12](#) and [13](#) respectively) subjects would be displayed under their actual dose, which could have been 200 mg, 400 mg or 600 mg CSL312.

Per Amendment 1 subjects will still be shown under their actual dose, but dosing modifications will not be permitted, and all subjects receive 200 mg CSL312. As no dosing modifications occurred before Protocol Amendment 1, all subjects will be shown under the actual dose level of 200 mg CSL312. Columns for 400 mg and 600 mg CSL312 will not be required. If there should be unplanned dosing different from the planned 200 mg CSL312, it will be discussed and documented during the PARM how this will be handled in the analysis.

For AE tables, treatment may be further differentiated by administration device in use when the AE started:

- 200mg CSL312 AI,
- 200mg CSL312 NSD,
- 200mg CSL312 Overall.

8 Data Handling Conventions

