8.2 General Derived Variables

8.2.1 Reference Dates and Study Days

Reference dates are used to assign study periods relative to treatment ([Section 8.4](#)). The main reference date for safety and efficacy is the treatment start date, which will be used to calculate study day for those measures.

The respective study day will be calculated as (date of interest - reference date) + 1 if the date of interest occurs on or after the reference date. If the date of interest occurs before the reference date, then the study day will be calculated as (date of interest – reference date). There will be no study day zero.

For PK, the reference date is the treatment start date.

For the additional PK assessments performed for adolescents and the subset of CSL312-naïve subjects, the reference date/time is the start of administration of the Day 1 Visit dose for the subset of CSL312 naïve subjects and the Month 3 dose for adolescents. The respective study day relative to the reference date will be calculated for figures as (date of interest - reference date) if the date of interest occurs on or after the reference date.

The reference date/time for treatment while on AI will be derived based on the dosing data and the Autoinjector confirmation page of the eCRF, as the first recorded dose date/time with date on or after the date on the Autoinjector confirmation page.

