8.4 Study Periods Relative to Treatment

AEs, HAE attacks, laboratory data, vital signs and other measurements will be assigned to the study time periods defined below.

Table 3 Definitions of Study Periods Relative to Treatment

Period	Start Date	End Date
Screening Period	Date of Informed Consent	Run-in Period Start Date
Run-in Period	Run-in Period Start Date	Day 1 Visit date of the Treatment Period or Date of Run-in Non-completion [whichever is first]
Treatment/Efficacy evaluation period	Date of Day 1 Visit of Treatment Period	Date of EOT Visit or EOS date [whichever is first]
Treatment/Efficacy before transition to AI evaluation period	Date of Day 1 Visit of Treatment Period	Date of first dose with AI – 1 Day (see Section 8.2.1)
Treatment/Efficacy after transition to AI evaluation period	Date of first dose with AI (see Section 8.2.1)	Date of EOT Visit or EOS date [whichever is first]
Follow-up	Date of EOT Visit	Date of Final/ Follow-up Visit
Safety evaluation period	Date and start time of First CSL312 Administration as entered in the eDiary	Date of Final/ Follow-up Visit
Safety Evaluation before transition to AI evaluation period	Date and start time of First CSL312 Administration as entered in the eDiary	Date of first dose with AI – 1 Day (see Section 8.2.1)
Safety Evaluation after transition to AI evaluation period	Date of first dose with AI (see Section 8.2.1)	Date of Final/ Follow-up Visit

The EOS date is the date entered in the Conclusion of Subject Participation eCRF page and should generally be identical to the date of the Follow-up Visit.

The handling of any unplanned dose changes or device changes will be discussed in the PARM. The safety evaluation period consists of the Treatment/Efficacy evaluation period plus the Follow-up Period.

Screening and Run-in periods will not be performed for roll-over subjects, instead relevant endpoint data (such as HAE attacks during the Run-in period) will be used from the CSL312_2001 and CSL312_3001 studies.

The duration of the Efficacy evaluation and the Safety evaluation period in days will be calculated as:

End Date – Start Date + 1 Day.

Screening, Run-in and Follow-up periods in days will be calculated as:

End Date – Start Date.

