For CSL312-naïve subjects to assign events starting on Study Day 1 to the Run-in or Treatment/Efficacy evaluation period the start time of the event will be compared to the time of the first dose to determine if the event took place prior to the first dose (leading to assigning the event to Run-in) or after the first dose (leading to assigning the event to the Treatment/Efficacy or Safety evaluation period).

In the case that a non-CSL312-naïve (rollover) subject has an event recorded in this study that takes place prior to first treatment in this study, it will not be assigned to a period but still displayed in listings.

9 Study Population

Unless otherwise stated, all tables and listings in this section will be based on the Screened Analysis Set.

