11.2 Adverse Events – Coding and Definitions

TEAEs are AEs which start on or after the date and time of the first administration of study treatment. TEAEs occurring until the Follow-up Visit will be summarized.

Where AE start dates and/or times are missing or partially missing, AEs will be assumed to be treatment-emergent, except if the partial start dates and/or times or the AE end date and/or time indicate that the AE started before the first administration of IP.

Table 4 TEAE Assignment in Case of Missing AE Start Date Elements

Missing elements of AE start	Rule	
Regardless of any missing information for AE start: AE end date / time < first IP start date / time		non-TEAE
Otherwise (ie, if AE end date / time \geq first IP start date / time or AE end date is missing, or AE is ongoing)		
- all		TEAE
- day and month	AE start year \geq IP start year	TEAE
	AE start year < IP start year	non-TEAE
- day	AE start month / year \geq IP start month / year	TEAE
	AE start month / year < IP start month / year	non-TEAE
- time	AE start date \geq IP start date	TEAE
	AE start date < IP start date	non-TEAE

Similarly, for subjects who transitioned to AI, where start dates and/or times of a TEAE are missing will be assumed to be on AI, except if the partial start dates and/or times or the AE end date and/or time indicate that the AE started before first dose with AI. The AI reference date/time will be used instead of the IP start date/time (see [Section 8.2.1](#)).

All reported AEs regardless of when they occurred will be listed.

COVID-19 associated AEs will be identified using the COVID-19 SMQ and will generally be included in TEAE tables identified by their standard MedDRA coding.

If for a TEAE the relationship to study treatment is missing the worst case will be assumed for summarizing analysis (ie, the relationship to study treatment will be assumed to be “Yes”). If the AE or SAE with missing relationship started before the first injection of study treatment it will be considered as “not related” (realistic case). No other imputations for missing AE information will be done.

AEs will be coded using MedDRA. There will be periodic updates of the MedDRA version. The latest licensed version will be used, and version updates will be implemented upon availability. AEs will be primarily classified by MedDRA PT. Analyses will be performed by SOC and PT. Aggregated incidences at SOC level and any TEAE will also be provided.

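### SAP Table 3 places adverse events that began before the injection on the switch date in the autoinjector period, against the SAP's own device-at-onset rule

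*SAP*

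**What the plan says.** SAP Section 8.4 introduces Table 3 with the statement that "AEs, HAE attacks, laboratory data, vital signs and other measurements will be assigned to the study time periods defined below". In that table the NSD safety period closes at "Date of first dose with AI – 1 Day (see Section 8.2.1" and the AI safety period opens at "Date of first dose with AI (see Section 8.2.1". Both limits are calendar dates. In the same table, the overall safety period opens at the date and start time of the first administration, so clock time is used for the first dose but not for the switch.

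Other parts of the SAP use time or onset:

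- Section 7.1, for AE tables: "treatment may be further differentiated by administration device in use when the AE started".
- Section 8.2.1 derives a reference date and time for AI treatment, "as the first recorded dose date/time with date on or after the date on the Autoinjector confirmation page".
- Section 8.4, for Study Day 1 events in CSL312-naïve subjects: "the start time of the event will be compared to the time of the first dose". It has no matching rule for the switch date.
- Section 11.2, for subjects who transitioned: "where start dates and/or times of a TEAE are missing will be assumed to be on AI", except where the partial start or the AE end shows onset before the first AI dose. The AI reference date and time takes the place of the first-dose date and time in Table 4.

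Sections 11.3 and 11.4 present TEAEs overall, on AI and on NSD. The Section 11.4 set includes laboratory findings reported as AEs.

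**The concern.** On the switch date, the subject is still under NSD dosing until the AI injection is given. A whole-day boundary puts those hours in the AI period, so an AE that arose on NSD can be counted against AI. Two programmers following different sections of this SAP could produce different AI and NSD tables from the same data.

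The switch date is also a day of concentrated ascertainment. The protocol requires the first AI dose to be given at the site. A scheduled switch visit includes a physical examination, vital signs, urinalysis and AE recording. The device split is a planned presentation of the primary endpoint, with device-specific injections and subject-years as denominators, so its assignment rule should give a single answer.

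**Working it through.** The plan states no figure on this point, so the check applies each rule to the same events. Assume, for illustration only, an AI dose at 10:00 on the switch date.

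| AE | Table 3 | Sections 7.1 and 8.2.1 | Section 11.2 |
|---|---|---|---|
| Starts the day before | NSD | NSD | not needed |
| Starts 08:00 on the switch date | AI | NSD | not needed |
| Starts 11:00 on the switch date | AI | AI | not needed |
| Switch date, start time missing | AI | cannot be placed | AI, unless it ended before 10:00 |
| Start wholly missing, ended 09:00 on the switch date | cannot be placed | NSD | NSD |

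The second row is the conflict. The last row shows how odd it is: an AE with no recorded start that ended at 09:00 goes to NSD, while a fully timed AE from 08:00 to 09:00 goes to AI under Table 3. SAP Sections 7 and 11.4 also put the most recent dose, with device and date, in the listings. The 08:00 event would be listed against NSD and tabulated under AI.

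**Incomplete dates.** For a transitioned subject, a month-and-year start goes to AI if it is the switch month and to NSD if earlier. A year-only start goes to AI if it is the switch year and to NSD if earlier. With the day missing, the NSD days that default to AI number (day of month of the switch − 1): 15 − 1 = 14 for a switch on the 15th, with a range of 0 to 30. With only the year known, the maximum is 364 days (365 in a leap year).

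**Switch-visit assessments.** Protocol Table 4 (Section 8.6.1) requires vital signs before the injection on the same day, so those findings precede AI by design. Under Amendment 1, blood is drawn on the dosing day with no stated order relative to the dose. Hematology, biochemistry and coagulation panels fall at Months 12, 24 and 36 and at End of Treatment, so a panel coincides with a switch only at Month 12 or 24. A Month 18 or 30 switch has urinalysis but no such panel, and an unscheduled switch visit has no other assessments. On urinalysis, the protocol says: "Urine collection for urinalysis will be collected for the last time at the visit that the subject consents to Amendment 1".

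Share of scheduled AI-period samples that are switch-day samples, for a switch at a scheduled visit:

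- Urinalysis: 1 of 1.
- Panels, Month 12 switch ending at Month 24 (Days 361 and 721): 1/2 = 50%.
- Panels, Month 12 switch ending at Month 36 (Days 361, 721 and 1081): 1/3 = 33%.
- Panels, Month 24 switch ending at Month 36 (Days 721 and 1081): 1/2 = 50%.

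These are shares of samples, not of AEs.

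**Subject-time.** Section 8.4 computes the safety period as end − start + 1; I assume this also holds for the device sub-periods. Take a Day 361 switch and a final visit on Day E. NSD time is 360 − 1 + 1 = 360 days and AI time is E − 361 + 1 = E − 360 days. They sum to E, which matches the overall period. If NSD time instead ended on Day 361, the sum would be 361 + (E − 360) = E + 1, one day too many per switcher. The whole-day boundary is therefore right for subject-years and wrong only for placing events.

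**The case against.** The strongest reply is that device attribution of AEs has its own rules in Sections 7.1, 8.2.1 and 11.2, that these use time, and that Table 3 is a whole-day device for durations. On that view, one clarifying sentence would be enough. This is partly right, and it defeats the inference that the SAP has settled on sending every switch-date event to AI: that is Table 3 read alone. But Section 8.4 says in terms that AEs are assigned to the Table 3 periods, so the contradiction is real. The Planned Analyses Review Meeting does not clearly resolve it either, since Section 8.4 refers unplanned changes there and this switch is planned.

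Four other stronger readings do not hold:

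- A reader might infer that all TEAEs with incomplete start dates go to AI. Section 11.2 limits the default to transitioned subjects and exempts events shown to have started before AI. Sending the remainder to the newer device is a prespecified convention; preferring another is a matter of judgement.
- A reader might take the 33% to 100% sample shares as shares of misassigned AEs. No event counts are given. A laboratory value becomes an AE only if judged clinically significant, a diagnosis is recorded in preference where known, and the documents do not say that a laboratory AE starts on the sampling date.
- A reader might infer that NSD loses its last laboratory assessment. Section 11.5 summarizes laboratory values by visit, with no device split stated.
- A reader might infer that all switch-visit findings belong to NSD. An injection-site finding after the first AI dose at the site belongs to AI.

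The listings would let a careful reader spot a misplaced event, which softens the consequence without correcting the table.

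**Conclusion.** The concern holds in a limited form. Table 3, as written, places AEs that began on the switch date before the AI injection in the AI period, contrary to the device-at-onset rule and the AI reference date and time elsewhere in the SAP. For a timed event, the exposure to error is at most the part of one calendar day before the dose, per switcher. Findings from pre-injection assessments at a scheduled switch visit are included if the AE is dated to that day, which is an assumption.

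Only the AI/NSD split of TEAE counts and rates is affected. The overall TEAE summary is unchanged, Section 10.2.1 does not divide efficacy by device, and the protocol plans no hypothesis testing. The number of affected events cannot be computed from the documents, so a material bias in the device comparison is not shown. The case for change is that the rule misclassifies as written and is nearly free to correct.

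**What to change.** Separate the boundary for events from the boundary for time:

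1. In Section 8.4, state that AEs are assigned by the Section 8.2.1 AI reference date and time. A switch-date AE whose start time precedes the AI dose is NSD, and one starting at or after the dose is AI. Cross-refer to this from Sections 7.1 and 11.2.
2. State that an AE first identified from an assessment or sample taken on the switch date before the AI dose is NSD. Repeat this in Section 11.2; otherwise the row of Table 4 for a missing time would return such an AE to AI. Section 11.5 already lists sampling date and time, so the comparison is feasible for laboratory findings.
3. Keep the existing minus-one-day limit in Table 3 for computing subject-years, so that NSD and AI time still sum to the overall time.
4. Keep the Section 11.2 default for start dates that cannot be placed. A sensitivity table assigning those TEAEs to NSD is optional.

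The cost is a few sentences in the SAP and a few lines of derivation code. No new data collection is needed for events with recorded times.

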9.1 Subject Disposition

A summary of subject disposition will be provided by CSL312 200 mg AI, CSL312 200 mg NSD, and overall, for the Screened Analysis Set. This summary table will include the number and percentage for the following:

- Subjects who provided informed consent,
- Subjects rolling over from studies CSL312_2001 and CSL312_3001,
- CSL312-naïve subjects screened,
- Screen failed subjects with reason for screening failure,
- Subjects who entered Run-in Period,

- Subjects discontinued during Run-in Period with reason for discontinuation (percentage based on number of discontinued subjects),
- Subjects not assigned to study treatment,
- Subjects assigned to study treatment,
- Subjects entered the Treatment Period,
- Subjects treated using the respective device (NSD or AI)
- Subjects who discontinued the study while using the respective device (NSD or AI) with reason for discontinuation (percentages based on number of discontinued subjects),
- Subjects who prematurely discontinued the study treatment while using the respective device (NSD or AI) with reason for discontinuation (percentages based on number of discontinued subjects),
- Subjects who completed the respective treatment while using the respective device (NSD or AI),
- Subjects who completed the study,
- Subjects in each of the analysis sets defined in [Section 6](#),
- Subjects in each of the subgroups defined in [Section 8.3](#).

Discontinuations due to COVID-19 will be included as a specific reason for discontinuation. Reasons for study withdrawal and study treatment discontinuation will be presented in the order they are displayed in the eCRF.

The following listings will be provided:

- Subjects included in analysis sets and reasons for exclusion from analysis sets.
- Subject discontinuations.
- Disposition (date of informed consent, date of eligibility for Run-in, date of entering treatment period, date of first and last study drug administration, whether the subject participated for at least one month in the treatment period. EoT date, EOS date, whether subject transitioned to AI and date of transition, reason for treatment discontinuation and/or study discontinuation).

9.2 Protocol Deviations

All identified protocol deviations throughout the study will be listed prior to DBL and will be classified into minor/major by CSL. Major protocol deviations are defined as deviations that could have a significant effect on the subject's safety, rights, or welfare and/or on the integrity of the study data.

The protocol deviations' classification into minor and major will be reassessed under statistical considerations. During the PARM, the classification and the subject's assignment to

the analysis sets will be discussed in detail. The Planned Analysis Review report will include these decisions and classifications and will be approved before each data-cut for interim analyses and prior to DBL for final analysis.

Possible major protocol deviations especially include the following but are not limited to:

Potential Major Protocol Deviations	Potential Exclusion From Analysis Set
Subject did not provide informed consent (informed consent date missing)	Screening, Safety, ATS, PP, PK, PD
Subject assigned to treatment but not treated with study treatment	Safety, PP, PK, PD
Subject assigned to treatment and treated but does not have at least one measurable PK concentration	PK
Subject assigned to treatment and treated but does not have at least one PD measurement	PD
Subject assigned to treatment and treated but violated inclusion or exclusion criteria	PP, potentially others to be discussed during the PARM
Subject assigned to treatment and treated but treatment compliance outside 80-120%	PP, potentially also PK, PD
Subject assigned to treatment and treated but received prohibited concomitant medication	PP, potentially also PK, PD

Presumably other protocol deviations will be classified as major and lead to the exclusion of subjects or data from analysis sets.

Prior to the PARM, a list of concomitant medications used in the study will be provided to CSL as an Excel file in the same format as the corresponding listing of concomitant medications in the table, figure, and listing (TFL) shells. This Excel file will be reviewed by CSL and concomitant medication potentially interfering with the PK/PD analysis or with the efficacy analysis will be flagged. Subjects with such a concomitant medication flagged may be excluded from the respective analysis set.

The following listings will be provided using the Screened Analysis Set:

- Planned and actual treatment.
- Protocol deviations with an indication whether it is major and any action for analysis, including exclusion from specific analysis sets.

